Thus, we aim to clarify whether HCQ relieves nonalcoholic steatohepatitis by reviewing medical records from our out-patient-clinic patients who accept the treatment of hydroxychloroquine (Plaquenil®).

A

B

Design : Retrospective study

Review medical records from patients who accept the treatment of hydroxychloroquine (Plaquenil®), find those with nonalcoholic steatohepatitis and observe the effects of hydroxychloroquine on them.

Methods :

Step 1 : screen out our targeted group : patients with nonalcoholic steatohepatitis

1. We have made a request to Information Technology Office of National Taiwan University Hospital, and this request is about the list of our out-patient-clinic patients who accept the treatment of hydroxychloroquine.
2. Collect and review the medical records, ultrasound and blood tests of patients in the abovementioned list and screen out those with nonalcoholic steatohepatitis based on the following criteria.

Inclusion criteria :

Our patients who taking hydroxychloroquine and match the following criteria

- A. Patients with fatty liver, based on the abdominal ultrasound report of which the date is the closest to the initial date of using HCQ.
- B. ALT level of 2.5 and 0.5 month prior to hydroxychloroquine treatment > 41 U/L
- C. With ALT result which is tested in 3 months after using HCQ.
- D. The initial date of taking HCQ is prior to September, 26, 2022, which is the date we got the list from Information Technology Office of National Taiwan University Hospital.

Exclusion criteria :

Our exclusion criteria can be separated into loose exclusion criteria and strict exclusion criteria.

Loose exclusion criteria : patients who match the following criteria will be excluded from the above group.

- A. Diseases of the biliary tract : the abdominal ultrasound report indicated the patient with stones in the biliary tract, or the patient with jaundice or his total bilirubin > 2.0 mg/dl
- B. Viral hepatitis : HBV Viral Load + or HCV Viral Load +
- C. Alcoholic steatohepatitis : History of drinking alcohol or AST/ALT > 1.5 and GGT > 2X
- D. Autoimmune hepatitis : ANA 1:80+ (above) or AMA+ anti-LKM+ or anti-SMA+
- E. Wilson's disease : ceruloplasmin < 20 mg/dl

Strict exclusion criteria : patients who had ever had viral hepatitis or was being infected by virus (HBV, HCV infection : HBsAg+ or anti-HBc+ or anti-HCV Ab+) will be further excluded from the above group.

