The definition of months : used in the criteria evaluation and the data analysis

Before patients used HCQ :

- 0.5 month : During the periods from one month prior to the date of initial use of HCQ to that date, we define the date which is the closest to 0.5 month as -0.5 month.
- 2.5 months : During the periods from four months to one month prior to the date of initial use of HCQ, we define the date which is the closest to 2.5 months as -2.5 months.
- 5.5 months : During the periods from seven months to four months prior to the date of initial use of HCQ, we define the date which is the closest to 5.5 months as -5.5 months.

After patients used HCQ :

- 0.75 months : During the periods that patients used HCQ for 0-1.5 months, we define the date which is the closest to 0.75 months as 0.75 months.
- 3 months : During the periods that patients used HCQ for 1.5-4.5 months, we define the date which is the closest to 3 months as 3 months.
- 6 months : During the periods that patients used HCQ for 4.5-7.5 months, we define the date which is the closest to 6 months as 6 months.
- 9 months : During the periods that patients used HCQ for 7.5-10.5 months, we define the date which is the closest to 9 months as 9 months.
- 12 months : During the periods that patients used HCQ for 10.5-13.5 months, we define the date which is the closest to 9 months as 12 months.

Then, in addition to the above-mentioned criteria, we will record the following two things separately.

The first one is hemochromatosis. Hemochromatosis may also cause hepatitis, but the prevalence of this disease in Taiwan is very low. Thus, we do not list hemochromatosis in the exclusion criteria.

The second one is drug-induced hepatitis. We do not list suspected drug-induced hepatitis in the exclusion criteria since drug-induced hepatitis may not be accurately confirmed based on our current medical records. However, if we find patients using drugs which may be related to hepatitis, we will record their information separately, including the duration of using these drugs and the ALT levels after stopping using it.

Step 2 : collect and analyze patients' medical information

(These patients are those with NASH and accept the treatment of HCQ)

We plan to collect the following information of each patients

1. The date when each patient started to take HCQ
2. Birth date :
To realize how old the patients were when they started to take HCQ.
3. Gender
4. Historical blood test results :

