 - A. ALT, AST, GGT, α -fetoprotein, platelet, FIB-4, WBC, bilirubin, albumin
 - a. For recording baseline demographics
 - b. To assess and analyze the status of hepatitis and liver fibrosis in each patient.
→ We plan to observe the ALT levels prior to the initial use of HCQ and ALT levels after it, and we will further analyze whether the ALT levels were decreased after patients took HCQ.
 - B. HbA1c*
 - a. For recording baseline demographics
 - b. To assess whether patients have diabetes mellitus
 - C. TG, TCHO*
 - a. For recording baseline demographics
 - b. To assess whether patients have hyperlipidemia

* We need these tests to realize whether patients have these comorbidities, since these are the risk factors of NASH.

Statistical Analysis Plan

1. We plan to use the statistical function of excel and Prism to analyze our results.
2. Initially, we will make the tables about the baseline demographics of patient who in our study group (patients with NASH and accept the treatment of HCQ), which we may use excel to help us arrange and analyze the tables.

- Then, we will check each patient's ALT levels in different month (prior to or after the initial use of HCQ), and we will use the date of initial use of HCQ as day0 and make box plots and violin plots to show the change of ALT levels with times going. We plan to use Prism to make the plots and analyze whether ALT levels were significantly decreased after patients took HCQ.

Members of our team

Position in this study	Name	Organizational Affiliation
Study Director	[name]	Graduate Institute of Pharmacology, College of Medicine, National Taiwan University
Study Principal Investigator	[name]., Ph.D.	1. Graduate Institute of Pharmacology, College of Medicine, National Taiwan University 2. Department of Internal Medicine, National Taiwan University Hospital

	Name	Organizational Affiliation	Phone and E-mail
Central Contact Person	[name]	Graduate Institute of Pharmacology, College of Medicine, National Taiwan University	[contact] E-mail : [contact]

References

- Pouwels, S., et al., *Non-alcoholic fatty liver disease (NAFLD): a review of pathophysiology, clinical management and effects of weight loss*. BMC Endocr Disord, 2022. **22**(1): p. 63.
- Niture, S., et al., *Emerging Roles of Impaired Autophagy in Fatty Liver Disease and Hepatocellular Carcinoma*. Int J Hepatol, 2021. **2021**: p. 6675762.

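### The 12-month rule selects the ALT closest to 9 months, so it always takes the earliest draw in its window, and a start-date draw counts as both pre- and post-HCQ

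*Combined protocol and SAP*

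**What the plan says.** The section on the definition of months sets eight windows, three before and five after the start of HCQ. Its heading gives their scope: "The definition of months : used in the criteria evaluation and the data analysis". Each rule names a window, a target time and a label, and takes the date nearest the target.

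The fourth post-treatment rule reads "During the periods that patients used HCQ for 7.5-10.5 months, we define the date which is the closest to 9 months as 9 months", which puts the target at the middle of its window. The fifth and last keeps that same target although its window opens later: "During the periods that patients used HCQ for 10.5-13.5 months, we define the date which is the closest to 9 months as 12 months".

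Two windows meet at the start of treatment. The pre-treatment one is defined as "During the periods from one month prior to the date of initial use of HCQ to that date", with a target half a month before the start. The post-treatment one that follows has zero as its lower limit: "During the periods that patients used HCQ for 0-1.5 months". Its target is 0.75 months.

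The Statistical Analysis Plan adds "we will use the date of initial use of HCQ as day0" but assigns that day to neither side. Inclusion criterion B relies on two of the pre-treatment windows: "ALT level of 2.5 and 0.5 month prior to hydroxychloroquine treatment > 41 U/L". The documents give no rule for ties or for dates on a window boundary.

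**The concern.** This is a retrospective chart review with unscheduled blood tests, and ALT is to be plotted and tested by month label. The window rules are therefore what decides which value enters the analysis when a patient has several.

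The 12-month rule has a target outside its own window. Followed literally, it is a first-draw rule, and the values labelled 12 months come systematically early in patients tested more than once.

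The start-date overlap puts the same draw on both sides of the before-and-after comparison. If blood was taken before the first dose that day, an untreated value can be shown as the first on-treatment value. The abstract reports an immediate fall in liver enzymes, and the 0.75-month point bears most directly on that claim.

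**Working it through.** **Inputs.** Windows, targets and labels come from the definition of months. The documents do not say how often ALT was measured, so the number of draws per window (k = 1 to 4) and their uniform timing are assumptions made for illustration.

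**Step 1: target against window midpoint.**

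| Label (months) | Window | Midpoint | Stated target |
|---|---|---|---|
| −5.5 | −7 to −4 | −5.5 | −5.5 |
| −2.5 | −4 to −1 | −2.5 | −2.5 |
| −0.5 | −1 to 0 | −0.5 | −0.5 |
| 0.75 | 0 to 1.5 | 0.75 | 0.75 |
| 3 | 1.5 to 4.5 | 3 | 3 |
| 6 | 4.5 to 7.5 | 6 | 6 |
| 9 | 7.5 to 10.5 | 9 | 9 |
| 12 | 10.5 to 13.5 | 12 | **9** |

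Seven of the eight targets equal the midpoint. The 12-month target does not, and it is the only one outside its window.

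**Step 2: what the 12-month rule returns.** For any t in [10.5, 13.5], |t − 9| = t − 9, which increases with t. The nearest date to 9 is therefore always the earliest draw; this needs no assumption. Example: draws at 10.6, 12.0 and 13.2 months lie 1.6, 3.0 and 4.2 from 9, so the rule takes 10.6. A target of 12 takes 12.0.

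**Step 3: size, for k independent uniform draws in the 3-month window.**

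- Mean time of the earliest draw: 10.5 + 3/(k+1). Mean time of the draw nearest 12: 12.0, by symmetry.
- The two rules agree only if all the other k − 1 draws fall later than the one nearest 12. Each does so with probability 1/2, so the rules differ with probability 1 − (1/2)^(k−1).
- Mean distance from 12 of the earliest draw: 3 × [0.5 − (1 − 0.5^k)/(k+1)]. For k = 2 this is 3 × [0.5 − 0.75/3] = 0.75.
- Mean distance from 12 of the nearest draw: 1.5/(k+1).

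| k | Different draw chosen | Mean time, as written | Mean time, target 12 | Mean distance from 12, as written | Mean distance from 12, target 12 |
|---|---|---|---|---|---|
| 1 | 0% | 12.0 | 12.0 | 0.75 | 0.75 |
| 2 | 50% | 11.5 | 12.0 | 0.75 | 0.50 |
| 3 | 75% | 11.25 | 12.0 | 0.84 | 0.375 |
| 4 | 87.5% | 11.1 | 12.0 | 0.94 | 0.30 |

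Simulation with 200,000 patients for each k agrees to within about 0.001.

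**Step 4: the start date.** At t = 0 a draw lies in [−1, 0] and in [0, 1.5], so it qualifies for both windows. It is 0.5 month from the −0.5 target and 0.75 month from the 0.75 target. In each case that is the largest distance the window allows, tied only with the opposite edge, so it is selected only where the window holds no closer draw. If it is the only draw in both windows, one ALT value serves as before and after, and that patient's change is exactly zero.

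**Step 5: other shared boundaries.** Neighbouring windows also share −4, −1, 1.5, 4.5, 7.5 and 10.5 months. A draw at exactly 10.5 months falls in both the 9- and the 12-month window, and the 12-month rule as written would always take it.

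**The case against.** The strongest reply is that the 9 is a copying slip with an obvious intent. The 12-month line repeats the one above it and still labels the result 12 months, so an analyst would probably use 12 and nothing would go wrong. The percentages apply only to patients with two or more tests in one three-month window, and that share is unknown. No eligibility criterion uses the 12-month window, and 12 months is not named as a key time point.

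On the start date, the windows sit under headings for before and after HCQ use, so a value known to be pre-dose arguably does not belong among the post-treatment values. Day 0 is also the least favoured date in each window. If HCQ lowers ALT, an untreated value at 0.75 months would dilute the apparent fall, not create one.

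Most of this stands as a limit on size. It does not remove the defect. Either the written rule is applied and 12-month values are mis-selected, or another rule is applied and the plan misdescribes the analysis. The headings help only where the order of blood draw and first dose is known, and the 0.75-month window still starts at 0 with no boundary rule. A bias towards no effect is still misclassification. The 12-month slip cannot alter eligibility, but the status of the start date does matter for criterion B, which uses the −0.5-month value.

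**Conclusion.** Both parts hold on the text. That the 12-month rule returns the earliest draw in its window is certain. Its consequence is nil for patients with one draw there and, under uniform timing, a mean shift of 0.5, 0.75 or 0.9 month for those with 2, 3 or 4 draws (12.0 minus 11.5, 11.25 and 11.1). These figures are conditional on the number of draws and are not proportions of the cohort.

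The start-date overlap is equally plain in the wording. Selection of one draw for both sides should be less common, because it requires no closer draw in either window; its frequency cannot be estimated from the documents. That the shared value is untreated assumes blood was taken before the first dose, which the documents do not state.

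No effect on ALT can be computed, since neither draw frequencies nor ALT data are given. The point should be corrected before analysis, as a clear error of modest and unknown consequence.

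**What to change.** Two changes in the definition of months:

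1. In the 12-month line, replace the target of 9 months with 12 months, as in the other seven rules.
2. Start the 0.75-month window on the day after the first HCQ date, so that a start-date draw counts only as pre-HCQ. The −0.5-month window, and hence criterion B, keeps its present wording.

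One further sentence would usefully assign each of the six other shared boundaries to a single window and say which draw is taken when two are equally close to the target.

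The cost is wording only, with no new data. If values have already been extracted, the 12-month selection needs re-running for patients with two or more draws between 10.5 and 13.5 months, and the 0.75-month value needs checking for anyone with a start-date draw.

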Study Protocol and Statistical Analysis Plan
Using hydroxychloroquine to treat nonalcoholic steatohepatitis

Study Title : Using hydroxychloroquine to treat nonalcoholic steatohepatitis

Study Principal Investigator (PI) : [name]., Ph.D.

Study Director : [name]

Objective : To examine whether hydroxychloroquine can treat nonalcoholic steatohepatitis effectively.

Abstract :

[figure not shown]
Nonalcoholic steatohepatitis (NASH) is a serious type of nonalcoholic fatty liver disease (NAFLD), which is characterized by lobular inflammation and apoptosis resulting from hepatic steatosis in the absence of excessive alcohol consumption[1]. If NASH are not controlled well, it will advance to liver fibrosis, cirrhosis[1], and even hepatocellular carcinoma[2]. However, there is no approved treatments currently.

According to guidance of American Association for the Study of Liver Diseases (AASLD) and a few studies, vitamin E and pioglitazone are two potential pharmacologic therapies for NASH. They have some therapeutic effects; however, they also have some safety concerns[3]. Therefore, those two drugs have not been widely used in clinical practices. In addition to vitamin E and pioglitazone, many drugs are being tested in clinical trials. However, promising results have not been revealed yet.

[figure not shown]
Recent clinical and experimental data suggested that hydroxychloroquine (HCQ) might improve metabolic profiles in patients or animals with obesity-related metabolic disorders[4, 5]. HCQ might also relieve liver inflammation in experimental animals with steatohepatitis[5]. As an inhibitor of endocytosis and autophagy with therapeutic effects in autoimmune disorders[6], it is reasonable to speculate that HCQ might also relieve liver inflammation in patients with steatohepatitis. Therefore, HCQ has been anecdotally prescribed to patients with steatohepatitis in our clinic. Excitingly, almost all those with HCQ treatment had immediate reduction of their liver enzyme levels, indicating instant relief of their steatohepatitis. Effects of HCQ were similar in those with negative anti-nuclear antibody (ANA) compared to those with weakly positive ANA (Figure A, B), suggesting that those are specific steatohepatitis-targeting rather than autoimmune-targeting effects from HCQ.

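### With a start date but no stop date, weight or other NASH treatment on the data list, the plan measures time since starting HCQ, not time on it, and cannot separate other causes of an ALT fall

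*Combined protocol and SAP*

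**What the plan says.** Step 2 sets out what will be collected for each patient. Item 1 is "The date when each patient started to take HCQ". Items 2 and 3 are birth date and gender. Item 4 is blood tests: "ALT, AST, GGT, α -fetoprotein, platelet, FIB-4, WBC, bilirubin, albumin", then HbA1c, triglycerides and total cholesterol. The list has no HCQ stop date, weight or concomitant NASH treatment.

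Under the definition of months, each post-treatment window is worded by duration of use; the 6-month window, for example, begins "During the periods that patients used HCQ for 4.5-7.5 months". The last window runs to 13.5 months. The Statistical Analysis Plan fixes the time origin differently: "we will use the date of initial use of HCQ as day0". The stated analysis is to "analyze whether ALT levels were significantly decreased after patients took HCQ", in one treated group, with no comparator and no adjustment.

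Two other places matter. The Abstract says that "vitamin E and pioglitazone are two potential pharmacologic therapies for NASH", and adds that safety concerns have kept both out of wide use. For drugs suspected of causing hepatitis, Step 1 records information "including the duration of using these drugs and the ALT levels after stopping using it".

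**The concern.** There are two separate gaps.

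The first is exposure. Months of use and months since first use agree only for patients who never stop. Entry requires an ALT around 3 months, and nothing in the criteria secures continued use at 6, 9 or 12 months. Without a stop date, a later ALT may be on or off HCQ and the dataset cannot say which. The plan records duration of use and ALT after stopping for other suspect drugs, but not for the drug under study.

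The second is attribution. The objective is whether HCQ treats NASH effectively, and the evidence is a before/after change. A patient who loses weight or starts another NASH treatment around day 0 contributes a fall that looks the same as an HCQ effect. With neither recorded nor excluded, the analyst cannot find such patients, set them aside or adjust for them.

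**Working it through.** The plan states no sample size, SD, effect size or stopping rate, so there is no figure of its own to reproduce. The check sets the collection list against the window definitions and then illustrates the size. **Every numerical input below is an assumption.**

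**1. Can the windows be built?** Yes. A start date and dated ALT results give elapsed time from day 0, so each draw can be placed in 0-1.5, 1.5-4.5, 4.5-7.5, 7.5-10.5 or 10.5-13.5 months. What cannot be established is that the patient was still taking HCQ, which the wording of the windows implies.

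**2. How many draws could be mislabelled?** If a constant share h stops per month, the share off drug by month t is 1 - (1 - h)^t.

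| h per month | month 6 | month 12 |
|---|---|---|
| 1% | 6% | 11% |
| 3% | 17% | 31% |
| 5% | 26% | 46% |

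**3. Which way does mislabelling push?** Suppose the true fall on HCQ is 20%, a share p is off drug, and ALT in those patients has returned to baseline. The geometric mean fall is then 1 - 0.8^(1 - p).
- p = 20%: 1 - 0.8^0.8 = 16.3%.
- p = 40%: 1 - 0.8^0.6 = 12.5%.

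That is dilution. If HCQ is inert, the same formula gives 1 - 1^(1 - p) = 0, so mislabelling alone creates no fall. The opposite direction arises if patients who stop go on to lose weight or start another treatment, because their later fall is then counted as treated. The plan's data cannot show which applies.

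**4. How large a fall could other causes produce?** Let HCQ be inert, and let a share f of patients have ALT lowered by a proportion e from weight loss or another treatment. The geometric mean fall is 1 - (1 - e)^f.

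| f | e = 20% | e = 40% |
|---|---|---|
| 10% | 1 - 0.8^0.1 = 2.2% | 1 - 0.6^0.1 = 5.0% |
| 30% | 1 - 0.8^0.3 = 6.5% | 1 - 0.6^0.3 = 14.2% |

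A simple mean of percentage changes, f × e, gives 2% (0.1 × 0.2) to 12% (0.3 × 0.4).

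**5. Would such a fall reach significance?** Take an SD of change of 30 U/L and two-sided alpha of 0.05. Let a share q of patients have a fall of d U/L from another cause, with zero HCQ effect. The mean fall is qd, the total SD is s = √(30² + q(1 - q)d²), and the chance of a significant fall is Φ(qd√n/s - 1.96).
- q = 10%, d = 20: mean fall 2 U/L, s = √936 = 30.6. The chance is about 6% at n = 30 and 10% at n = 100.
- q = 40%, d = 30: mean fall 12 U/L, s = √1116 = 33.4. The chance is about 50% at n = 30 and 95% at n = 100.

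The nominal rate in that direction is 2.5%.

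**The case against.** The strongest reply is that the day-0 rule already settles the windows. On its natural reading every draw is kept by elapsed time, and draws after stopping tend to dilute a real effect rather than inflate it. This largely stands. A reader might infer from the missing stop date that the windows cannot be applied, or that the omission itself credits other causes to HCQ. The documents support neither. The omission misclassifies exposure, while confounding by co-treatment or weight loss comes from the one-group design and the items not collected.

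A reader might also infer that patients who stop for lack of response drop out of later windows and exaggerate the fall. If 20-40% stopped, those with worse ALT change were 2-3 times as likely to do so, and the SD of log-ALT change were 0.4, on-HCQ draws alone would show a fall of roughly 3-10% under an inert drug, and 22-28% when the true fall is 20%. The plan states no restriction to on-HCQ draws, so these figures do not describe it. They do show why such a restriction should not be the main analysis.

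On co-treatment, the plan says the two named drugs are little used, and treatment that was stable from well before baseline would not by itself produce a before/after fall. Both points stand. They limit the drug share without making it zero, and they do not touch weight.

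Nor is the plan without any relevant data. Three pre-HCQ windows give a view of the prior trend, HbA1c and lipids are collected, and suspected hepatotoxic drugs are recorded. These help only in part. A pre-HCQ trend cannot reveal a change that began alongside HCQ, the metabolic tests are meant for baseline and comorbidity status, and no analysis use is stated for the drug records.

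**Conclusion.** The point holds in two limited parts. First, the windows show time since HCQ start rather than confirmed time on HCQ, and off-drug ALT is labelled as treated, with bias possible in either direction. Second, weight and concomitant NASH treatment are neither collected nor excluded, so a fall from those causes cannot be separated from an HCQ effect. The illustrative size of the second part is an apparent fall of 2-14% from an inert drug. It rests wholly on the assumed 10-30% affected and 20-40% lower ALT, neither of which is anchored in the documents. HCQ indication is also missing from the list, but the documents give no basis for sizing its effect, so nothing here rests on it. The changes are worth making because they cost little, but they will not turn a before/after series into evidence of efficacy.

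**What to change.** Reword the post-treatment windows as time since HCQ start, in line with the day-0 rule, and state that all draws stay in the main analysis.

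Add to the Step 2 list, from the charts already under review:
- HCQ stop date and reason;
- weight nearest each window, where recorded;
- start and stop dates of vitamin E, pioglitazone and any other NASH treatment.

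Name the baseline versus 3-month ALT comparison explicitly, since the Statistical Analysis Plan specifies no test. Then add three sensitivity analyses:
- (a) on-HCQ draws only;
- (b) the baseline versus 3-month comparison without patients who started another NASH treatment between -4 and +4.5 months, the span from the opening of the -2.5-month window to the close of the 3-month window. Note that this conditions on a post-baseline event, since poor responders may be likelier to start something else;
- (c) the same comparison adjusted for weight change, where available.

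State that these checks do not replace a comparator. The cost is a little more abstraction work, some missing weights, and a main estimate that may be smaller because it includes patients who stopped.

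### The only planned before-after test is on ALT, the marker patients are selected on; AST, GGT, platelets and FIB-4 are collected but get no analysis of change

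*Combined protocol and SAP*

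**What the plan says.** The Objective is "To examine whether hydroxychloroquine can treat nonalcoholic steatohepatitis effectively". The design is a retrospective review of one group of HCQ-treated patients, with no comparator.

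Inclusion criterion B requires "ALT level of 2.5 and 0.5 month prior to hydroxychloroquine treatment > 41 U/L". Criterion C adds "With ALT result which is tested in 3 months after using HCQ". AST and GGT enter selection only through the alcohol exclusion: "History of drinking alcohol or AST/ALT > 1.5 and GGT > 2X".

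Step 2, item 4A lists "ALT, AST, GGT, α -fetoprotein, platelet, FIB-4, WBC, bilirubin, albumin". Its purposes are (a) baseline description and (b) "To assess and analyze the status of hepatitis and liver fibrosis in each patient". The arrow under (b) describes a before-after comparison for ALT only.

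Item 2 of the Statistical Analysis Plan plots ALT over time and will "analyze whether ALT levels were significantly decreased after patients took HCQ". It names no change analysis for any other marker.

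The month definitions include an earlier pre-treatment window, four to seven months before HCQ: "we define the date which is the closest to 5.5 months as -5.5 months". That value plays no part in entry, and the plan does not name it as the reference for the test.

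**The concern.** Patients chosen because ALT was high on two dates include some whose ALT was only temporarily high. Their later values tend to drift down whatever the treatment. ALT is both the selection variable and the only tested outcome, so it takes this regression to the mean directly.

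The other markers are to be collected for hepatitis and fibrosis but play no stated part in judging change. The Abstract already takes a fall in liver enzymes as relief of steatohepatitis, so a significant ALT result could readily be reported as an effect on the disease. At stake is whether the result can bear on the Objective at all, and whether the fibrosis purpose in item 4A(b) is ever addressed.

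**Working it through.** The plan states no sample size, SD, effect size or alpha, so there is no figure of its own to reproduce. The check is a comparison of the text followed by an illustration on assumed inputs.

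**1. Role of each marker in the plan**

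| Marker | Entry threshold of its own | Planned before-after test |
|---|---|---|
| ALT | Yes, > 41 U/L twice | Yes |
| AST | No (alcohol exclusion only, as AST/ALT) | None |
| GGT | No (alcohol exclusion only) | None |
| Platelets, FIB-4 | No | None |

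**2. ALT under no drug effect.** The model is log ALT = stable patient level + independent visit deviation. Assumed: source median 45 U/L, total log SD 0.5, between-patient share of variance 0.65. The visit SD is 0.5 × √(1 − 0.65) = 0.296. Keep patients with both pre-treatment values above 41 U/L. By simulation, the mean deviation at -0.5 month among those kept is 0.0834; at 3 months it is 0. Expected change = exp(−0.0834) − 1 = **−8.0%** (geometric mean 66.7 to 61.4 U/L).

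**3. A second marker without a threshold.** Let r be its visit-level correlation with ALT and k its log SD divided by that of ALT. Expected change = exp(−0.0834 × r × k) − 1.

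| r | k = 1 | k = 1.5 |
|---|---|---|
| 0.3 | −2.5% | −3.7% |
| 0.5 | −4.1% | −6.1% |
| 0.7 | −5.7% | −8.4% |
| 0.9 | −7.2% | −10.7% |

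Simulation runs agree to within about 0.1 percentage point (for instance −2.4% in some runs at r = 0.3). The marker falls more than ALT whenever r × k exceeds 1; at k = 1.5 that means r above 0.67. The model leaves out the alcohol exclusion and does not treat GGT separately.

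**4. How often the second marker falls with no drug effect.** With k = 1 and an assumed 100 patients, its mean falls in about 72%, 84%, 92% and 97% of studies at r = 0.3, 0.5, 0.7 and 0.9. The fall is significant (two-sided 0.05) in about 9%, 17%, 30% and 46%.

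**5. Range for ALT.** Take source medians of 30, 41 and 60 U/L, log SDs of 0.5 and 0.7, and between-patient shares of 0.6, 0.75 and 0.9. The no-effect fall in ALT from -0.5 to 3 months then runs from 1.2% to 19.2%. In the central case (41, 0.5, 0.75) it is 6.3%. A paired test on log ALT would call that fall significant in 27% of studies of 50 patients and 49% of studies of 100.

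**6. The -5.5 month reference.** In all these scenarios the no-effect change in ALT from -5.5 to 3 months is about 0%, because neither value is used for selection. This rests on stable patient levels and independent visit variation.

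**The case against.** Item 4A(b) speaks of status in each patient, and the arrow directly beneath it confines the analysis to ALT, so the other markers may be meant only to characterise patients. The Objective does not mention fibrosis, and the documents state no final conclusion. Criterion C guarantees only a post-HCQ ALT; nothing shows that AST, GGT or platelets were measured on the same dates or at 12 months. The -5.5 month window is already defined for use in the data analysis, and the plots already cover months before HCQ.

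Much of this stands. It limits how far the plan can be said to leave a stated question unanswered, it makes availability of the extra markers uncertain, and it shows that a more direct check on selection is close at hand. It does not remove the gap: item 4A(b) lists analysis of hepatitis and fibrosis separately from baseline description, only ALT gets one, and the -5.5 month value is not the named reference.

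A reader might infer that ALT is certainly the most distorted marker, or that a parallel fall in AST and GGT would show that selection is not the cause. The documents support neither. They give no variances or correlations, AST and GGT enter the alcohol exclusion, and the illustration shows both markers falling together with no drug effect.

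**Conclusion.** The point holds, and the plan should be changed. ALT is the only marker with an entry threshold and the only one with a planned test of change. Without a comparator, some fall in ALT is expected from selection, and a fall in ALT alone supports no statement about NASH or fibrosis.

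The size is illustrative: about 8% on the main assumptions, and 1.2% to 19.2% across the wider set. AST and GGT are probably less affected, which depends on their relative variability and on an imperfect correlation with ALT. Adding them reduces reliance on the selected marker; it does not remove regression to the mean. Nor does the calculation show that an observed ALT fall would be wholly an artefact.

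**What to change.** - In item 2 of the Statistical Analysis Plan, name AST and GGT as secondary outcomes, analysed in the same windows as ALT where measured, with the number of patients with paired values at each window.
- Report platelets and FIB-4 before HCQ and at 12 months, as descriptive.
- Name the -5.5 month ALT as a reference for the ALT change, and report how many patients have it.
- Word the conclusion as a change in liver enzymes after HCQ start. Make no statement on fibrosis from ALT, and do not treat a fall in AST or GGT of any size as proof that selection is ruled out.

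The cost is some additional tables from markers already on the collection list. The downsides are more secondary tests, which need a stated order or a label as supportive; incomplete values in retrospective records; and a more cautious conclusion.
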